#### **6.7 Summary of Overall Risks and Benefits**

Although the clinical benefit of OP-1250 has not yet been established, modulation of the ER is a well validated target and forms the basis for standard of care treatment. Nonclinical data support the hypothesis that OP-1250 may be more efficacious than current, approved therapies. The intent of this study is to begin to understand the safety, PK, and preliminary evidence of activity. If appropriate, OP-1250 would be studied in Phase II and Phase III trials to demonstrate meaningful therapeutic benefit to patients.

Subjects will be carefully monitored for tumor response and symptom relief in addition to safety and tolerability. Estrogen antagonists commonly have adverse effects consistent with estrogen depletion, most notably, hot flashes and vaginal dryness.

Most OP-1250-related findings in the preclinical toxicology studies were consistent with the pharmacological mechanism, antagonism of ER in tissues, as well as changes in reproductive organs in males and females (ovary, vagina, uterus, mammary glands, prostate, seminal vesicles, testes, and epididymis). Between the rat and dog studies, there was generally good concordance of target organs specifically for changes in reproductive organs, hematological parameters, liver, adrenal glands, and spleen. Most drug-related findings had correlative effects between anatomic changes and monitorable peripheral changes (hematology, clinical chemistry). OP-1250-related effects to the retina were observed in the rat study only.

Most adverse findings in rats and dogs occurred at dose levels that also had adverse or noteworthy findings in the in-life data, specifically body weight, food consumption, or clinical signs (tremors). Therefore, the adverse anatomic findings had premonitory effects that were detected as general health assessments.

A key feature of OP-1250 is the long plasma half-life that resulted in persistent systemic exposure for the entire 28-day treatment-free recovery period. Since the animals were exposed to OP-1250 for the duration of the recovery phase, few of the toxicities fully reversed.

In the GLP toxicology studies, the HNSTD was 30 mg/kg in rats and 30 mg/kg in dogs after 28 daily oral doses. Since most of the effects of OP-1250 in animal models are pharmacologically related, reflecting excessive pharmacology or findings secondary to excessive pharmacology, and can be monitored clinically, the initiation of clinical trials at

pharmacologically relevant doses is expected to be safe. Only at the highest dose of OP-1250 tested, (100 mg/kg), were retinal abnormalities seen in a single species (rats). No retinal toxicities were seen in rats at the next lowest dose tested in rats (30 mg/kg) and no retinal abnormalities were seen at any dose in beagle dogs. OP-1250 is an amphiphilic cationic drug, similar to tamoxifen, and these retinal changes in the rat may be due to its chemical structure. In this trial, dose of OP-1250 expected to be efficacious is well below the comparable dose in which retinal changes were observed in rats.

There have been 4 events of grade 4 neutropenia in the Phase Ia of the study. The protocol has been amended to add additional complete blood count assessments. In addition, grade 4 neutropenia and decreased neutrophils are considered adverse events special interest (AESI).

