### 3.1 Schedules of Events

**Table 1: Schedule of Events for All Subjects**

Assessments	Screening	Treatment Period (28-Day [4-Week] Cycles)												EOT Visit Within 42 days after last IP dose	Safety Follow-up At 30 to 42 days after EOT Visit		
		≤ 28 days	C1					C2				C3 and subsequent odd Cycles				C4 and subsequent even Cycles	
			D1	D2	D8	D15	D22	D1	D8	D15	D22	D1	D15			D1	D15
Visit window				± 2 d	± 2 d	± 2 d	± 2 d	± 2 d	± 2 d	± 5 d	± 2 d	± 5 d	± 2 d				
General eligibility/safety assessments																	
Obtain informed consent	X																
Medical history	X																
Demographics	X																
Physical examination 	X	X		X	X			X		X		X		X			
ECOG performance status	X	X		X	X			X		X		X		X			
Vital signs, height  , weight	X	X		X	X			X		X		X		X			
Triplicate 12-lead ECG 	X	X	X	X	X			X		(C3, C5, C7, C9 only)							
AE recording 		X	X	X	X			X		X		X		X			
Prior and concomitant medications and therapies 	X	X	X	X	X			X		X		X		X			
Investigational product																	
Dispensing and compliance check of OP-1250 and drug diary			X	X	X			X		X		X		X			
OP-1250 return and compliance check				X	X			X		X		X		X			
OP-1250 administration in clinic at study site		X	X	X	X			X		X		X		X			

Assessments	Screening	Treatment Period (28-Day [4-Week] Cycles)												EOT Visit Within 42 days after last IP dose	Safety Follow-up At 30 to 42 days after EOT Visit
		≤ 28 days	C1					C2				C3 and subsequent odd Cycles			
Visit window		D1	D2	D8	D15	D22	D1	D8	D15	D22	D1	D15	D1	D15	
				± 2 d	± 2 d	± 2 d	± 2 d	± 2 d	± 2 d	± 2 d	± 5 d	± 2 d	± 5 d	± 2 d	
Laboratory assessments															
Pregnancy test (WOCBP only) 	X	X					X				X		X		X
Hematology  and serum chemistry 	X	X		X	X	X (CBC only)	X (CBC only)	X (CBC only)	X (CBC only)	X (C3/C5 only)	X (C3 only; CBC only)	X (C4 only; CBC only)		X	
Fasting lipid profile 	X														
Coagulation	X														
Urinalysis 	X														
OP-1250 PK 		X	X	X	X		X				X (C3, C5, C7, C9 only)				
██████████	X														
██████████	X									X (C3 only)					X
Biopsy and disease assessment															
Radiology examination 	X										X 			X 	
Tumor measurement	X										X 			X 	
██████████	X	X									X (C3 only)			X	
Safety follow-up															

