In vitro, OP-1250 inhibits CYP2C8 and CYP2C9 in a time-dependent manner and may reduce the clearance of CYP2C8 substrates (eg, repaglinide) and CYP2C9 substrates (eg, [S]-warfarin). At clinically relevant concentrations, OP-1250 does not induce drug metabolizing enzymes.

OP-1250 may inhibit P-gp (P-glycoprotein) and breast cancer resistance protein (BCRP) in the intestine and increase the bioavailability of P-gp substrates (eg, digoxin) and BCRP substrates (eg, sulfasalazine). The P-gp and BCRP inhibition of OP-1250 is limited to the intestine and OP-1250 is not an inhibitor of other common drug transporters. OP-1250 is not a substrate of P-gp, BCRP, OATP1B1, OATP1B3, or OCT1.

In vitro, OP-1250 appears to be a substrate, primarily of CYP3A4, and as such its exposure may be increased by strong CYP3A4 inhibitors (eg, itraconazole) and reduced by strong CYP3A4 inducers (eg, rifampin). OP-1250 is poorly soluble at a high pH but is freely soluble at a pH of 3. Because of the pH-dependent solubility of OP-1250, in this initial study, agents such as proton pump inhibitors (PPIs) should be avoided because they increase the normal acid pH of the stomach and may affect the pharmacokinetics (PK) of OP-1250. The bioavailability of OP-1250 when combined with drugs that affect gastric pH is being determined in a study of healthy volunteers. OP-1250 was evaluated in a comprehensive preclinical toxicology program in rats and dogs dosed for up to 28 days. OP-1250-related toxicities were dose-related and consistent with systemic exposure.

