In the Good Laboratory Practice (GLP) toxicology studies, the highest non-severely toxic dose was 30 mg/kg in rats and 30 mg/kg in dogs after 28 daily oral doses. Since most of the effects of OP-1250 are pharmacologically related and can be monitored clinically, the initiation of clinical trials at pharmacologically relevant doses is expected to be safe. Only at the highest dose of OP-1250 tested, (100 mg/kg) were retinal abnormalities seen in a single species (rats). No retinal toxicities were seen in rats at the next lowest dose tested in them (30 mg/kg) and no retinal abnormalities were seen at any dose in beagle dogs. In this trial, the dose of OP-1250 expected to be efficacious is well below the comparable dose in which retinal changes were observed in rats. OP-1250 is an amphiphilic cationic drug and these retinal changes in the rat may be due to its chemical structure. Tamoxifen is also an

amphiphilic cationic molecule and retinal abnormalities have been reported with tamoxifen. Rat retinal pigment epithelium was packed with crystalline-like inclusions at high doses of tamoxifen exposure (Lüllmann 1981). The exact incidence of tamoxifen retinal changes in humans is not known, but over 2 years at 20 to 30 mg daily, 1.5% to 15% of patients, respectively, showed retinal changes and tamoxifen at standard doses is generally well tolerated (Al-Tweigeri 1996).

A comprehensive review of OP-1250 is contained in the Investigator's Brochure (IB) supplied by Olema Pharmaceuticals. The investigator should review this document prior to initiating this study.

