#### **8.10 Dose Modification for Phase I and Phase II**

All AEs should be assessed according to the NCI-CTCAE, v 5.0. In the event of multiple toxicities, dose delays and modifications should occur in accordance with the highest grade AEs observed.

Institutional guidelines should be followed in the event of hypersensitivity reaction.

Subjects who experience a DLT or any of the following AEs in Cycle 2 and beyond will have study drug treatment interrupted. Dose modification will be allowed as per [Table 8](#). Modified dose levels are shown in [Table 9](#).

Dose Modification Guidelines for Intermediate Doses are presented in [Table 10](#). The first dose reduction will be approximately 20% to 30%, the second dose reduction is

approximately 40% to 50%, and the third dose reduction is approximately 70% to 80%. Dose reductions below 15 mg daily are not allowed.

Dose modifications will only be made for TEAEs that are not clearly due to disease progression or extraneous causes.

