13.4 Clinical Laboratory Evaluation

Local laboratories will be used for laboratory safety evaluations in this study. Laboratory parameters (serum chemistry and hematology) will be summarized using descriptive statistics at baseline and at each post-baseline time point. Changes from baseline will also be summarized.

The following laboratory parameters will be graded according to CTCAE v5.0: hemoglobin, platelets, neutrophils, alkaline phosphatase, AST, ALT, creatinine, glucose, lactate dehydrogenase (LDH), potassium, sodium, and total bilirubin. Shift tables assessing changes from baseline to the maximum post-baseline CTCAE grade will also be presented.

The incidence of CTCAE grade ≥ 3 serum chemistry and hematology results will also be summarized for the parameters listed above.

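### Table 1 schedules no blood count or chemistry between Cycle 5 Day 1 and the end-of-treatment visit, so late symptom-free laboratory toxicity is not routinely looked for

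*Protocol*

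**What the plan says.** Protocol Section 6.7 reports the signal, "There have been 4 events of grade 4 neutropenia in the Phase Ia of the study", and the response, "The protocol has been amended to add additional complete blood count assessments". It gives no number, timing or end date for the added counts. Section 9.2 makes Grade 4 neutropenia and Grade 4 decreased neutrophils the only events of special interest.

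In Table 1 the hematology and chemistry row is dense in Cycles 1 and 2. From Cycle 3 the cells carry their own limits:
- Day 1 of odd cycles: Cycles 3 and 5 only.
- Day 15 of odd cycles: "X (C3 only; CBC only".
- Day 1 of even cycles: "X (C4 only; CBC only".
- The next entry is the end-of-treatment visit.

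Footnotes 7 and 8 and Section 10.2.6 add no later scheduled test.

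Section 8.10 sets the action rule without an end date: "Subjects who experience a DLT or any of the following AEs in Cycle 2 and beyond will have study drug treatment interrupted". Table 8 then acts on ANC, platelets, creatinine, bilirubin and AST/ALT. Section 8.11 allows treatment for up to one year, and longer by agreement. SAP Section 13.4 plans this summary: "Shift tables assessing changes from baseline to the maximum post-baseline CTCAE grade will also be presented". It also plans the incidence of Grade 3 or higher results.

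**The concern.** Table 8 can act only on a value that someone has measured. Grade 4 neutropenia without fever, or a transaminase rise without symptoms, gives no reason to order an unscheduled test. If it first arises after Day 113, daily dosing continues. Some Table 8 rules also depend on duration, such as AST or ALT above 5 times the upper limit of normal for at least 14 days, and these need serial values.

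The documents give no reason to expect laboratory toxicity to appear only early. Section 6.2 describes a "comprehensive preclinical toxicology program in rats and dogs dosed for up to 28 days", and adds that exposure persisted through the recovery period and few toxicities fully reversed. Section 6.2 also names hematology and clinical chemistry as the peripheral changes that can be monitored. In addition, Section 8.8.4 lets active Phase I subjects move to 120 mg. A subject who moves from 60 mg after Cycle 5 doubles the dose with no scheduled count or chemistry afterwards.

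Two things are at stake: the safety of subjects on long treatment, and the completeness of the laboratory tables.

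**Working it through.** The plan states no figure to reproduce. The check is a reading of one table row followed by day arithmetic.

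**Reading the row.** Table 1 has 16 visit columns, and the row as extracted from the PDF shows 15 cells. Counted from the right, the entries from Cycle 3 to end of treatment align with their columns, and their labels name the cycles. The missing cell therefore lies between C1D22 and C2D22 and does not affect this point.

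**Inputs.** Cycle length is 28 days (Section 10.5.2). The last scheduled test on treatment is C5D1 (Table 1). Treatment lasts up to one year and beyond (Section 8.11). The end-of-treatment visit is within 42 days of the last dose (Section 10.5.3).

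**Day of the last scheduled test.** 4 × 28 + 1 = Day 113, after 16 completed weeks (112 days).

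**Share of treatment time T without a scheduled test.** (T − 112) / T:

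| Time on drug | Days without a scheduled test | Share | Days if end-of-treatment visit is 42 days after last dose |
|---|---|---|---|
| 24 weeks (168 days) | 56 | 33% | 98 |
| 32 weeks (224 days) | 112 | 50% | 154 |
| 1 year (365 days) | 253 | 69% | 295 |
| 2 years (730 days, assumed) | 618 | 85% | 660 |

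The share passes one half only beyond 32 weeks.

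**Typical treatment length.** Protocol Section 6.1 quotes median progression-free survival of 2.8 months (exemestane alone), 5.7 months (placebo plus fulvestrant) and about 6.5 months (second-line fulvestrant). If time on OP-1250 resembled these, which is an assumption, then at 30.4375 days per month (SAP Appendix A):
- 2.8 months = 85 days, which ends before C5D1, so there is no gap.
- 5.7 months = 173 days; (173 − 112) / 173 = 35%.
- 6.5 months = 198 days; (198 − 112) / 198 = 43%.

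**Effect of the change.** Day 1 tests from Cycle 6 to Cycle 13 add 8 draws in a one-year treatment and cut the longest on-treatment gap from 253 days to 28. Testing on Day 1 of odd cycles only (C7, C9, C11, C13) adds 4 draws and leaves gaps of 2 × 28 = 56 days.

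**The case against.** **Section 6.7 and Table 1 agree.** A reader might infer a contradiction between them. The documents do not support that. Section 6.7 promises additional counts without saying how many or for how long, and Table 1 contains them in the early cycles. The gap concerns late monitoring only.

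**Late events can still be detected.** A reader might infer that they cannot. That is also too strong. The synopsis and Section 8.17.2 provide for additional laboratory tests when clinically indicated. Visits with symptom-directed examination and adverse event recording continue. Section 10.2.6 has clinically significant abnormal results repeated at the investigator's discretion, and the restart conditions in Table 8 require recovery values. Symptomatic cases and abnormalities already known are therefore covered. What remains is the first-onset, symptom-free event.

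**The early emphasis may be deliberate.** The four events came from escalation up to 300 mg, and neither their doses nor their timing is given. The selected dose is 120 mg. Section 8.8.4, on 37 Phase Ib patients, names two Grade 3 events as the exceptions to Grade 1 or 2 and reports no dose reductions for adverse events. This has some weight, but the length of follow-up is not stated, so it says little about events after Cycle 5.

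**The nonclinical text can be read the other way.** The statement that "most of the effects of OP-1250 are pharmacologically related and can be monitored clinically" supports starting clinical trials, not a year of surveillance, and Section 6.2 says adverse anatomic findings were preceded by signs visible on general health assessment. That is fair, but it does not show that blood count or chemistry changes always come with symptoms.

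**SAP Section 13.4 also summarizes by time point,** which shows where scheduled data stop. This is true of the by-visit tables. The worst-grade and Grade 3 or higher tables collapse over time and do not show it.

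**Conclusion.** The point holds as a gap in late routine monitoring. Followed as written, the plan has no scheduled hematology or chemistry from Day 113 until the end-of-treatment visit, while the rules and the event of special interest that depend on those values continue. The share of treatment affected is 33% at 24 weeks, 50% at 32 weeks and about 69% at one year; it is most of the treatment only for subjects dosed beyond 32 weeks. SAP Section 13.4 can under-count late symptom-free events in its worst-grade and Grade 3 or higher tables.

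The size of that under-count cannot be stated. The documents give no rate or timing for late laboratory events, so any projected percentage of missed events would rest on invented risks. The conclusion assumes that sites follow Table 1 and do not add routine local testing of their own. The change is worth making because it is cheap and protects subjects on long treatment.

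**What to change.** In the hematology and chemistry row of Table 1, leave Cycles 1 to 5 as they are, remove the cycle limits on the later Day 1 cells, and schedule a complete blood count with differential plus chemistry on Day 1 of every cycle from Cycle 6 for as long as dosing continues. The minimum alternative is Day 1 of each odd cycle from Cycle 7; PK blood is already drawn at Cycles 7 and 9.

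The cost is a protocol amendment to one table row and one extra local-laboratory draw per cycle (8 in a one-year treatment, or 4 under the alternative), at visits that already take place. If the sponsor keeps the Cycle 5 limit, the protocol should give the reason, and SAP Section 13.4 should state that scheduled on-treatment laboratory data end at Cycle 5 Day 1.

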## 7 STUDY OBJECTIVES AND ENDPOINTS

The study objectives and the respective endpoints for each part of the study are presented in [Table 5](#).

**Table 5 Study Objectives and Endpoints**

Phase I (Part A [Dose Escalation] and Part B [Dose Expansion])	
Primary Objectives	Primary Endpoints

 
To identify the MTD and/or RP2D of OP-1250 (Part A [Dose Escalation]).
 
	
 
Incidence and nature of DLTs as defined Section 8.8.2.
 
MTD and/or RP2D of OP-1250 when used as a single agent.
 

 
To confirm the RP2D of OP-1250 (Part B [Dose Expansion]).
 
	
 
RP2D of OP-1250 when used as a single agent.
 

 
To assess the safety and tolerability of OP-1250 (Parts A [Dose Escalation] and B [Dose Expansion]).
 
	
 
Incidence, nature, and severity of TEAEs and SAEs according to NCI-CTCAE version 5.0.
 

 
To assess the PK of OP-1250 (Parts A [Dose Escalation] and B [Dose Expansion]).
 
	
 
Plasma levels of OP-1250 at pre-defined intervals to establish PK parameters (including: <math>C_{max}</math>, <math>C_{min}</math>, <math>T_{max}</math>, AUC, <math>t_{1/2}</math>, and OP-1250 trough concentration at steady state).
 

Secondary Objectives	Secondary Endpoints

 
To estimate the ORR defined as the CR + PR rate of OP-1250.
 
	
 
ORR by evaluation of tumor response assessments using RECIST 1.1 in subjects with measurable disease.
 

 
To estimate the CBR (CR + PR + SD <math>\geq</math> 24 weeks) of OP-1250.
 
	
 
CBR, as defined by percent of subjects with CR + PR + SD <math>\geq</math> 24 weeks, by evaluation of tumor response assessments using RECIST 1.1.
 

	

Exploratory Objectives	Exploratory Endpoints

	

	

	

	

Phase II	
Primary Objectives	Primary Endpoints

 
To estimate the ORR of OP-1250 in subjects with HR-positive/HER2-negative metastatic or locally advanced breast cancer with no evidence of CNS metastases who have progressed following at least 1 hormonal therapy regimen in the metastatic or locally advanced setting.
 
	
 
ORR by evaluation of tumor response assessments using RECIST 1.1 in subjects without evidence of CNS metastases who have measurable disease.
 

 
To assess the safety and tolerability of OP-1250.
 
	
 
Incidence, nature, and severity of TEAEs and SAEs according to NCI-CTCAE version 5.0.
 

 
To assess the plasma PK of OP-1250.
 
	
 
Plasma levels of OP-1250 at pre-defined intervals to establish PK parameters (includes <math>C_{max}</math>, <math>C_{min}</math>, <math>T_{max}</math>, AUC, <math>t_{1/2}</math>, and OP-1250 trough concentration at steady state).
 

Secondary Objectives	Secondary Endpoints

 
To estimate the CBR of OP-1250 in subjects with HR-positive/HER2-negative metastatic or locally advanced breast cancer with no evidence of CNS metastases who have progressed after receiving at least 1 hormonal treatment regimen in the metastatic or locally advanced setting.
 
	
 
CBR, as defined by percent of subjects with a CR + PR + SD for <math>\geq 24</math> weeks, by evaluation of tumor response assessments using RECIST 1.1 in subjects without evidence of CNS metastases.
 

	

[REDACTED]

Exploratory Objectives	Exploratory Endpoints

[REDACTED]

	

[REDACTED]

[REDACTED]

	

[REDACTED]

[REDACTED]

	

[REDACTED]

[REDACTED]

	

[REDACTED]

[REDACTED]

	

[REDACTED]

Abbreviations: AUC = area under the curve; C = Cycle; CBR = clinical benefit rate;  $C_{\max}$  = maximum concentration;  $C_{\min}$  = minimum concentration;

D = study day; DLT = dose-limiting toxicity; DoR = duration of response; EOT = end-of-treatment; ; ESR1 = estrogen receptor 1; HER2 = human epidermal growth factor receptor 2; HR = hormone receptor; iCBR = intracranial clinical benefit rate; MTD = maximum tolerated dose; *mut* = mutant; NCI-CTCAE = National Cancer Institute – Common Terminology for Adverse Events; ORR = overall response rate; PFS = progression-free survival; PIK3CA = phosphoinositide 3-kinase alpha catalytic subunit; PK = pharmacokinetic; PR = partial response;

RECIST = Response Evaluation Criteria in Solid Tumors; RP2D = recommended Phase II dose; SAE = serious adverse event; SD = stable disease;  $t_{1/2}$  = half-life; TEAE = treatment-emergent adverse event;  $T_{\max}$  = time to maximum concentration; *wt* = wild-type

See [Appendix E](#) for RECIST V1.1

## 8 INVESTIGATIONAL PLAN

### 8.1 Overall Study Design and Plan

This is a Phase I dose escalation and dose expansion and Phase II monotherapy open-label, first-in-human study to determine the dose limiting toxicity (DLT), maximum tolerated dose (MTD) and/or recommended Phase II dose (RP2D), to characterize the safety and pharmacokinetic (PK) profile, and to estimate the preliminary antitumor activity of OP-1250 as a single agent in adult subjects with hormone receptor (HR)-positive/human epidermal growth factor receptor 2 (HER2)-negative metastatic or locally advanced breast cancer. Treatment and study subject evaluation will be performed in 28-day cycles. This study comprises 2 Phases: Phase I (Part A [Dose Escalation] and Part B [Dose Expansion]) and Phase II.

**Phase I: Part A (Dose Escalation) and Part B (Dose Expansion):** This portion of the study will evaluate the safety and PK of a range of doses of OP-1250 administered orally to subjects and determine the MTD and/or RP2D. Part A will employ a rolling 6 dose escalation study design, whereby cohorts of 3 to 6 subjects will be sequentially enrolled and monitored for DLTs during the first cycle of study treatment. Part B will enroll approximately 30 subjects in the expansion phase at the RP2D, or in the event 2 dose levels are being considered for the RP2D, then approximately 30 subjects will be enrolled in each of the 2 dose levels. Approximately 42 subjects will be enrolled in Part A (dose escalation), and up to approximately 60 subjects will be enrolled in Part B (dose expansion). Up to a total of approximately 102 subjects may be enrolled in the Phase I portion of the study.

**Phase II:** This portion of the study further explores the clinical activity, safety, and PK of OP-1250 at the RP2D and will estimate the preliminary anti-tumor efficacy. Up to 88 evaluable subjects will be enrolled over 3 cohorts in the Phase II: Cohort A will enroll 50 subjects with measurable disease without evidence of CNS metastases (subjects in the expansion at the RP2D will be included in this cohort), Cohort B will enroll approximately 15 subjects with non-measurable (evaluable) disease without evidence of CNS metastases; and Cohort C will enroll approximately 15 subjects with CNS metastases. To allow for subject replacement up to a total of approximately 88 subjects may be enrolled in the Phase II portion of the study.

